#### **4.3 Baseline procedures**

Baseline data collection will begin after a subject gives consent to participate in the study. The SC or RA who conducted eligibility screening and obtained verbal consent will conduct the baseline interview questionnaire during the same enrollment call. Data collection will entail questionnaires and data abstracted from the

patient's medical record. The questionnaires will be administered in an interview format. Data abstracted from the patient's EHR in Epic will occur after the enrollment phone call.

After consent is obtained and baseline data is collected by the SC or RA, the SC/RA will randomize the patient and provide a video link and instructions on how to watch the video if the patient is randomized to watch it. This is to ensure that any RA who is blind to the patient's study arm remains blinded and is able to complete follow-up interviews.

#### **4.4 Intervention procedures (by visits)**

##### **1. Administering the BETTER from pain video (Full intervention and Video-only arms)**

At the end of the enrollment call, the SC/RA will send the video link to the participant via text on an encrypted study phone and/or by secure email. Patients are asked to watch the video within 24 hours of their acute care visit. Patients are asked to send their answers or number of correct answers to the video multiple-choice questions within 24 hours of their acute care visit. If the participant does not provide their answers to the multiple-choice questions within 24 hours, they will be placed into the intention-to-treat analysis and excluded from the per-protocol analysis.

##### **2. Conducting the telecare call (Full intervention arm)**

The full intervention group will also receive telecare following a protocol-guided phone call from a research nurse (RN) ~48 - 72 hours after study enrollment (or after discharge from the hospital if the subject was admitted) with an extension of 5 days if contact is not made within the 72-hour time frame. Thus, the RN will have a total of 7 days to contact the subject.

Prior to the call, the RN will review the EHR data abstraction instrument in REDCap, which provides a summary of the patient's medical visit, co-morbid conditions, allergies, prescribed medications, and a treatment plan. The RN will also review any pertinent notes in the EHR. The RN will then call the patient and proceed through the telecare script, addressing pain management goals, current analgesic use, and non-pharmacologic methods of pain management. Based on the patient's answers, the RN will make recommendations as needed. The patient's responses and the RN's recommendations will be recorded in REDCap under the telecare instrument as well as the number of minutes of the call.

The telecare call is designed to last ~15 minutes, and the RN will be trained on how to conduct the call. At the conclusion of the call, the RN will summarize their recommendations and encourage the patient to follow up with their PCP. Patients without a PCP will be provided a referral, including local free or low-cost medical clinics for uninsured patients.

##### **3. PCP Communication (Full intervention arm)**

Following the telecare call, the RN will enter a note in the subject's EHR that documents the patient's current clinical status, information reviewed, and any recommendations or referrals made. The RN will report the (1) Date, time, location and reason for the ED/OrthoNow visit; (2) Results of diagnostics studies; (3) Discharge prescriptions/recommendations; (4) Summary of and link to the video; (5) Summary of the telecare conversation; and (6) Encouragement for follow-up. If the patient's PCP is a UNC-affiliated provider, they will send the note through an electronic message in the EHR. If the patient's PCP is not affiliated with UNC, the RN will send the note via the US Postal Service. At the end of the note, PCPs will be asked to confirm the note has been received and reviewed by the PCP.

#### 4.5 Follow- up procedures (by time points)

Follow-up data will be obtained for subjects in all arms of the study by a RA who is blind to the subject's group allocation. Data collected at all follow-up time points will include a phone interview with the patient and data obtained from the patient's EHR. Prior to each phone interview, data will be extracted from the patient's EHR by an RA using standardized questions with explanations in REDCap.

**1-Week Follow-up:** This call can take place anytime from the 7th day through the 12th day after study enrollment (or hospital discharge if subject was admitted). Following the phone script, the RA will make a total of 10 attempts via phone call, text, or email to reach the subject for the follow-up interview. This phone interview will take ~20 minutes and include the questionnaires noted below. The purpose of this call is to assess the mechanisms that might contribute to patient recovery. However, some outcomes (pain, healthcare use) will also be assessed at this time point.

##### 1-week questionnaires

- Brief Pain Inventory-short form^28
- Patient Global Impression of ChangePreparedness and Confidence Questions
- Pain Self Efficacy Questionnaire 4-item^30
- Analgesic and Opioid use
- Other (Nonpharmacological) pain management strategies used
- Opioid-Related Symptom Distress Scale
- Pittsburg Sleep-2
- International Physical Activity Questionnaire-short form^33
- Healthcare Utilization Questions
- Opioid prescribed (obtained from EHR)

**Longitudinal Follow-up:** Follow-up data collection via phone interviews will occur at 30 days, 90 days, 180 days, and 360 days +/- 7 days following study enrollment. Following the phone script, the RA will make a total of 10 phone calls to reach the subject at each data point for the follow-up interview. These phone interviews will take ~20 minutes each and include the questionnaires noted below:

##### 1, 3, 6, and 12-month follow-up questionnaires

- Brief Pain Inventory-short form^28
- Patient Global Impression of Change
- PROMIS Global Health-Physical 2a
- PROMIS-Physical Function-4
- Pittsburg Sleep-2
- Analgesic and Opioid use
- Other (Nonpharmacological) pain management strategies used
- Opioid-Related Symptom Distress Scale
- Healthcare Utilization Questions
- Opioid prescribed (obtained from EHR)

#### 4.6 Withdrawal procedures

Subjects may withdrawal from the study at any time. If such a request is made, no further contact with the subject will be made. Data that was collected prior to withdrawal will be retained unless the subject requests that all data be removed from the study.

## Screen failure procedures

Subjects who fail the eligibility screening interview will be thanked for their time and informed they do not meet the criteria for the study. Data collected during the screening interview will be retained and used to report screen fail characteristics.

## 5 STUDY EVALUATIONS AND MEASUREMENTS (how measurements will be made)

### 5.1 Variables to be abstracted from medical charts

Summary of Data to be Abstracted from EHR at Baseline:

- Final diagnosis
- Final disposition (was patient admitted or not)
  - If patient was admitted, hospital discharge date
- Whether the patient was hospitalized up to 30 days before ED/OrthoNow visit.
- Comorbidity data will be abstracted in order to calculate a Gagne score.
- Treatment (any allergies to medications, medications prescribed, recommendations)
- Opioids and/or pain medications prescribed

Summary of Data to be Abstracted from EHR at Follow-up (1 week & 1, 3, 6, 12 month):

- Healthcare Utilization since last visit/call
  - Number of hospitalizations, days spent in hospital, name and location of hospital
  - Number of ER or Urgent Care visits, name of facility and location
  - Number of Primary Care office and telehealth visits and how many of the visits were with UNC providers
  - Number of non-physician (physical therapist, occupational therapist, chiropractors, etc.) visits
- Opioids prescribed

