#### Recruitment Exclusionary Criteria from EHR

- language other than English
- primary pain located in the head, chest, or abdomen
- pain due to ischemia, infection, or some other cause not due to MSP (blood clot, kidney stone, etc.)
- primary pain due to self-injury
- patient is critically ill determined by an acuity score of 1 in the ED tracking board
- diagnosis of somatoform disorder, schizophrenia, dementia, or bipolar disorder
- patient is a prisoner

**4.2 Eligibility Screening Interview:** The second step of the recruitment process, entails an eligibility screening interview and will occur for patients meeting the initial recruitment criteria noted above. Patients will be contacted by phone within 24 hours after their acute care visit. The purpose of the study will be explained, and verbal assent will be sought in order to conduct the eligibility screening interview. The inclusionary/exclusionary criteria addressed in the interview is noted below:

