#### **Objective 1:**

To evaluate the primary outcome by intervention arm, we will use a linear mixed model to conduct an analysis of covariance (ANCOVA), controlling for site type (ED vs. Urgent Care), index visit pain severity, age, gender, race, medical comorbidities (as the Gagne score), baseline intermittent opioid use, a history of chronic pain, and access to a PCP. These control variables were selected *a priori* based on prior evidence of prognostic value and will not be subjected to significance testing. This model will include all BPI-SF average scores (1, 3, and 6) as outcomes, will include fixed effects for group, time, and group-by-time, as well as all of the control variables, and will use an unstructured covariance matrix for the error terms. We will specify a 6 degrees of freedom (df) linear contrast to test the overall null hypothesis of no mean difference in BPI-SF score at any follow-up visit across the 3 groups at the 5% significance level. If the overall null hypothesis is rejected, we will then conduct separate 3 df contrasts to compare each of the intervention groups with the control group using a Bonferroni-adjusted 2.5% significance level. We will estimate mean pairwise differences along with 95% confidence intervals at each time point. Missing BPI-SF data will be ignored for the primary comparison. The primary analysis will be conducted using the ITT Population, but will also be repeated using the PP Population.

We will also conduct a sensitivity analysis of the primary comparisons using a multiple imputation approach. Pain scores for patients taking analgesics in the past week will be imputed using demographic characteristics, history of chronic pain, pain location, pain etiology (traumatic vs. not traumatic), baseline pain severity, analgesics used, and treatment group.

We will use similar ANCOVA models to test the intervention effects on the secondary outcomes. For continuous or ordinal outcomes, we will use generalized estimating equations models and contrast tests. For any binary variables (e.g., opioid use or non-use) we will also use ANCOVA model but will fit mixed-effect logistic regression models.

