For each outcome measured using a scale, missing scale items will be imputed as described in Section 5 above. Data missing by design (e.g., due to a skip pattern in the data collection form) will be filled in logically where appropriate.

7. Analysis of Participant Follow-Up

We will present an account of the final disposition (completed, withdrew, lost, or died) for each participant in the ITT Population, including any admission violations and group assignment. The number and proportion of participants in the ITT population who provided information for the analyses of the study objectives will be summarized by randomization group. Frequencies of participants with missing primary outcome data will be summarized by randomization group and study visit. We will provide a CONSORT diagram showing the flow of participants through the trial, indicating withdrawals by treatment arm with reasons, when provided.

8. Analysis of Baseline Data

We will summarize baseline data (i.e., pre-randomization data) for the ITT Population, by randomization group, site type (ED vs. Urgent Care), and overall. Measures of central tendency and dispersion for continuous and certain discrete variables will include means, standard deviations, medians, minima, and maxima. Categorical data will be summarized with frequencies and percentages. Some continuous variables may also be grouped into categorical levels and evaluated in frequency tables. No inferential statistics (i.e., p-values and/or confidence intervals) for comparing data between groups will be presented.

9. Primary Analysis of Primary Outcome (Objective 1)

The primary analysis of BPI-SF will use the ITT Population, and will be repeated secondarily using the Per-Protocol Population. We will use a linear mixed model to conduct an analysis of covariance (ANCOVA), controlling for site type (ED vs. Urgent Care), baseline pain severity, age, gender, race,

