comorbidity score, baseline intermittent opioid use, a history of chronic pain, and access to a PCP (access to a PCP was used to stratify the randomization and, as such, it is important to control for it in all models). These control variables were selected a priori based on prior evidence of prognostic value and will not be subjected to significance testing. This model will include all pain severity scores (1, 3, 6, and 12 months) as outcomes; will include fixed effects for group, visit, and group-by-visit; and will use an unstructured covariance matrix for the error terms. We will first test a 6 degrees of freedom (df) linear contrast of the overall null hypothesis of no mean difference in the primary outcome at any of the 1-, 3-, and 6-month follow-up assessments across the 3 groups at the 5% significance level. If the overall null hypothesis is rejected, we will then conduct two separate 3 df contrasts to compare each of the intervention groups with the control group using a Bonferroni-adjusted 2.5% significance level. We will secondarily estimate mean pairwise differences along with 95% confidence intervals at each time point, including data collected at the 12-month follow-up time point.

10. Secondary and Exploratory Analyses (Objective 1)

The same linear mixed modeling approach used for the primary outcome will be applied to each of the separate components of the BPI-SF (Pain Severity and Interference). Similar comparisons using the sequence of linear contrasts and 95% confidence intervals as specified for the primary outcome will be made.

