Similar longitudinal modeling approaches will be applied to evaluate treatment effects on other secondary outcome variables. Appropriate models will be applied depending on the scale of the outcome variable, but the model for fixed effects/linear component will remain consistent across outcomes. For opioid use, a binary outcome, we will apply generalized estimating equations along with a logistic link function and unstructured working covariance matrix. For analgesic-related side effect frequency and severity, physical function, overall health, sleep quality, and healthcare utilization, all quantitative measures, we will compare mean response over time by applying generalized estimating equations along with an identity link function and unstructured working covariance matrix. All comparisons will be made using appropriately specified linear contrasts, tested at the 5% significance level, and/or 95% confidence intervals.

Non-opioid analgesic use and use of other pain management strategies will be descriptively summarized by randomization group and time, without any plans to apply inferential statistical methods (hypothesis tests or confidence intervals).

Exploratory Analyses: To assess whether some groups of participants are more likely to benefit from the interventions, we will estimate and compare effects using tests of interaction for a priori identified subgroups based on gender, race, health literacy, access to a PCP, and preference for control over decision-making⁴. To assess for potentially differential intervention effects on the primary outcome across each of the subgroups, we will use ANCOVA models similar to that for the primary analysis, but with the addition of appropriate interactions between intervention groups and subgroups. Separate models will be used to assess each interaction. Interpretation of differential effects of the intervention will be limited to subgroups for which an interaction is significant at the 5% level.

⁴ After enrollment was converted to remote due to COVID, which meant that the intervention was experienced following the ED visit, the shared decision making items were dropped from the study. Thus, we will not use “preference for control over decision-making” as a variable in our models.

11. Assessing Potential Mechanisms (Objective 2)

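### The opioid-use model reuses the pain model's covariates and omits whether an opioid was prescribed at the index visit; the cost is some precision at early visits, not bias

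*Protocol*

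**What the plan says.** **The variable is collected.** Protocol 5.1 includes "Opioids and/or pain medications prescribed" in the baseline chart abstraction.

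**When it arises.** Protocol 4.2 says "Patients will be contacted by phone within 24 hours after their acute care visit", and Protocol 4.3 places consent, baseline interview and randomisation in that same call. The chart is read later ("EHR in Epic will occur after the enrollment phone call"), but the entry describes the visit that came before the call. SAP section 2 and its footnote, and the footnote on decision-making items in SAP section 10, show that before the remote conversion some participants were enrolled in person.

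**The covariates.** SAP section 9 fits the pain model "controlling for site type (ED vs. Urgent Care), baseline pain severity, age, gender, race", then "comorbidity score, baseline intermittent opioid use, a history of chronic pain, and access to a PCP". That makes nine covariates, the same as in Protocol 6.1, Objective 1. The only opioid term is intermittent use at baseline.

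**The opioid model.** SAP section 10 states: "For opioid use, a binary outcome, we will apply generalized estimating equations along with a logistic link function". It adds that "the model for fixed effects/linear component will remain consistent across outcomes", so the nine covariates carry over unchanged.

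**Stratification.** Protocol 3.2 and 8.1 stratify by PCP access and age group only.

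**The concern.** The covariate list was built for a pain outcome. For opioid use, whether the participant left the index visit with an opioid is plausibly a stronger baseline predictor of use at the next calls than most of the nine terms. It is neither a stratum nor a covariate.

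The term for intermittent use is not an obvious substitute. Daily users of more than two weeks are excluded, and on its face the term describes earlier occasional use rather than a new prescription.

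Reducing long-term opioid use is the first secondary objective in the Protocol synopsis, and Protocol 6.2 says that the sample size was not based on secondary outcomes. If prescribing happened to differ between arms, readers would ask for the adjustment, and adding it after unblinding would be post hoc.

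**Working it through.** **1. The plan's own figure.** No power is stated for opioid use. The enrolment figure does reproduce: 3 × 120 = 360, and 360 / (1 − 0.10) = 400, or about 133 per arm.

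**2. Inputs that must be assumed.** The documents give none of these: the share prescribed an opioid (f), later use in those prescribed (p1) and in the others (p0), and the treatment odds ratio (OR).

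**3. Size of a chance imbalance.** SE = √(2f(1 − f)/133).
- f = 0.25: √(0.375/133) = 5.3 percentage points.
- f = 0.50: √(0.5/133) = 6.1 points.

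With p1 = 0.30 and p0 = 0.05, a 1-SE imbalance moves the early difference between arms by SE × 0.25, which is 1.3 to 1.5 points.

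**4. Variance explained.** R² = f(1 − f)(p1 − p0)² / [p(1 − p)], where p = f·p1 + (1 − f)·p0.
- f = 0.25: p = 0.1125, R² = 0.0117/0.0998 = 12%.
- f = 0.50: p = 0.175, R² = 0.0156/0.1444 = 11%.
- Late visit, f = 0.40, p1 = 0.15, p0 = 0.05: p = 0.09, R² = 0.0024/0.0819 = 3%.

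**5. Power without and with the covariate.** These are two-arm logistic regressions at a single visit, Wald test at two-sided 5%, 4,000 runs each.

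| Visit | n per arm | f | p1 / p0 | OR | Without | With |
|---|---|---|---|---|---|---|
| Early | 122 | 0.35 | 0.20 / 0.05 | 0.35 | 46% | 47% |
| Early | 122 | 0.35 | 0.30 / 0.05 | 0.35 | 56% | 59% |
| Early | 122 | 0.35 | 0.50 / 0.05 | 0.35 | 61% | 72% |
| Early | 133 | 0.40 | 0.30 / 0.10 | 0.50 | 44% | 45% |
| Early | 133 | 0.40 | 0.50 / 0.05 | 0.50 | 38% | 48% |
| Early | 133 | 0.40 | 0.50 / 0.05 | 0.35 | 69% | 80% |
| Late | 107 | 0.40 | 0.15 / 0.05 | 0.50 | 20% | 19% |
| Late | 107 | 0.40 | 0.15 / 0.05 | 0.35 | 32% | 32% |

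A cruder check treats adjustment as raising n to n/(1 − R²), starting from 80% power. At 6 months (120 per arm, R² 0.002 to 0.05) power becomes 80 to 82%. Early (133 per arm, R² 0.12 to 0.36) it becomes 85 to 94%. The upper end needs 60% use in those prescribed against 5% in the others, a stronger link than any in the table.

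**6. Type I error over all randomisations.** With OR = 1 the model without the covariate rejected in 4.1 to 4.8% of runs, so there is no inflation.

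**7. Type I error given an imbalance.** Now fix a 12-point imbalance, about 2 SE (122 per arm, f = 0.35, p0 = 0.05, OR = 1). The model without the covariate rejected 8.8% of the time at p1 = 0.30, 14.8% at p1 = 0.50, and 5.2% at p1 = 0.15. At p1 = 0.30 and 0.50 the adjusted model stayed at 4 to 5%.

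**The case against.** **The tempting stronger reading.** A reader might infer that chance differences in prescribing distort the planned opioid comparison. The documents do not support that. Randomisation makes the comparison unbiased on average, and its standard error already allows for imbalance in covariates left out (step 6). What remains is precision, and the conditional behaviour in step 7, which matters only if a sizeable imbalance occurs.

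**The gain fades where the objective lies.** The objective concerns long-term use, and at 6 months the gain is about nil. This stands. The benefit is confined to early visits, although those visits do enter the longitudinal model.

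**The figures are assumed and the model simplified.** The plan is a three-arm longitudinal GEE that already adjusts for pain severity, site type, chronic pain and earlier opioid use, all of which may overlap with prescribing. This stands, so the early gains are likely on the high side.

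**Intermittent opioid use is undefined.** Protocol 5.2 asks at baseline about opioids taken in the ED and pain medicines over the past week, so the term might capture some visit-related exposure. This is a fair caution, but nothing says that it records a prescription to take home.

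**One list for all outcomes is deliberate.** It limits selection of covariates outcome by outcome. That is a sound reason, but a single addition prespecified before unblinding keeps the same protection.

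**Not every recorded prescription precedes randomisation.** Admitted participants (assumed up to 10%) may be prescribed opioids at hospital discharge, and in-person enrolees may have been randomised before the prescription was written. This stands and shapes the fix. The chart is also read after randomisation, and Protocol 8.2 lets unblinded staff collect record data, so the covariate needs a strict definition.

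**Conclusion.** The omission is real: a baseline value that the trial already collects, and that plausibly predicts early opioid use, is missing from the opioid-use model. Its consequence is modest. Under the assumed rates, adding it gains about 1 to 11 points of power at early visits, with the upper end requiring that about half of those prescribed are still using an opioid, and about nothing at 6 months. It also guards against a chance imbalance in the trial actually run.

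It would be wrong to conclude that the opioid analysis is biased or that its error rate is inflated. It would also be wrong to expect much improvement for long-term use. The primary BPI-SF result is not touched. The change is worth making because it is cheap and is credible only if made before unblinding.

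**What to change.** In SAP section 10, before unblinding, add one fixed covariate to the opioid-use GEE, or at minimum to a prespecified supportive version of it: opioid prescribed at the index ED/OrthoNow visit, issued before randomisation (yes/no, from the baseline chart abstraction).

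- Do not count prescriptions issued at a later hospital discharge for admitted participants.
- Give participants enrolled in person before the remote conversion a separate level, so that no post-randomisation value is adjusted for.
- Record the change in the SAP, which provides for documented changes (opening statement) and for decisions in blinded review (section 4).

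The cost is a short SAP entry and derivation of one variable from data already abstracted. The odds ratio becomes conditional on a tenth covariate, and there is slightly more sparse-data risk if late opioid use is rare. In-person enrolees, whose number the documents do not give, get no prescription adjustment.
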